## **8. Risks**

### **Potential Risks:**

Potential risks of this study include loss of confidentiality, time involvement, fatigue, distress, and embarrassment because of the nature of some of the questions. There are no physical risks to participants who receive the nurse case management intervention. All participants will be informed about the potential risks of participating.

Questioning participants about socially stigmatized conditions accompanied by low level of knowledge among the general population, such as HIV and HCV, is sensitive. There is a risk that a participant is not aware of his or her HCV diagnosis at the time of enrollment; however, participants will be told about the study by their primary HIV provider or self-referred from study flyers that list current chronic HCV infection in the eligibility criteria. Therefore, it is unlikely that a participant will be unaware of an HCV diagnosis at the time of study enrollment. While learning about HCV and HCV-related liver disease may be distressing to participants, studies evaluating HCV educational interventions have not reported any negative effects of providing HCV education to persons with chronic HCV and have demonstrated that HCV education improved patient outcomes. The research nurse case manager will emphasize participants' strengths, benefits of HCV treatment, and HCV cure. The study's research nurse also has experience providing education about HCV to

Date: May 8, 2017

Principal Investigator: [name], MPH, NP

Application Number: IRB00081068

newly diagnosed patients. In the event that participants become distressed or uncomfortable during a study visit, the study team will stop the study and the participants' primary HIV provider will be called to assess the participant. Participants will be allowed to withdraw from the study at any time.

Initiating a discussion about drug interactions and the need to make modifications to an ART regimen could turn participants away from HCV care if they do not want to make a modification. However, the purpose of this intervention is to foster a supportive environment to make these modifications easier for the patient. Participants would eventually be approached by the HCV or HIV provider with the need for ART modification regardless of participation in this study in order to initiate HCV therapy; therefore, this study is not expected to generate any additional risks of distress or loss to follow-up than usual care, and may decrease distress associated with this process due to supportive and timely care coordination.

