### 4. Study Procedures

Date: May 8, 2017

Principal Investigator: [name], MPH, NP

Application Number: IRB00081068

The proposed study is a single blinded, randomized controlled trial. The trial will evaluate a nurse case management intervention and determine differences in linking to HCV care (primary aim) and time to HCV treatment initiation (secondary aim) among persons co-infected with HIV. Patients with HIV and chronic HCV infection will be recruited from the Johns Hopkins University AIDS Service (JHUAS). After informed consent, participants will be randomized to a standard nurse case management protocol or enhanced usual outpatient care (100 per group), described below. Information flyers, provider referral, and targeted mailings will be used for recruitment.

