**Recruitment:** Patients will either 1) self-refer by contacting the research team after seeing flyers posted in the Bartlett Specialty Practice waiting room or in an exam room research binder; 2) be referred from their HIV provider in clinic; 3) self-refer after receiving a targeted letter in the mail; or 4) self-refer after finding the study on clinicaltrials.gov, Trials @ Hopkins, or referral from the CFAR Hotline. Eligible prior study participants from the Principal Investigator's SUSTAIN study (NA\_00079147) who agreed to be contacted for future research (HIPAA form 3) will also be called. On a weekly basis, Bartlett Specialty Practice appointments will be reviewed electronically in EPIC to identify HIV/HCV co-infected patients scheduled for primary care visits. Letter notifications will be mailed to potentially eligible patients who have an upcoming appointment inviting them to contact the study team to participate in the research study. Daily, the primary HIV provider, registered nurse, or certified medical assistant will be approached to refer his or her eligible patients to the study. After the patient has contacted our research team to meet at the Bartlett Specialty Practice, a member of the study team will provide information regarding the study, answer any questions, and obtain informed consent. The PI will be available in person or via telephone to answer any questions when a student is present for the consent. Once enrolled, the study team will assign a study identification number (SIN) to the subject. This will be the primary mode of identification throughout the study. The SIN will appear on the consent form, the questionnaire, as well as all data collection forms. As part of the informed consent document, the participant will receive information on how to contact the investigators to discuss any of the nurse case management intervention components.

**Eligibility:** Adults who are co-infected with HIV and HCV who have not attended an HCV-specific appointment in the past year will be enrolled in the proposed study. Specific eligibility requirements are detailed in inclusion/exclusion criteria below.

Date: May 8, 2017

Principal Investigator: [name], MPH, NP

[figure not shown]
Application Number: IRB00081068

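### The risk section's reason for calling unawareness of the HCV diagnosis unlikely does not cover patients first contacted by letter or telephone

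*Combined protocol and SAP*

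**What the plan says.** Section 8, Potential Risks, states the hazard directly: "There is a risk that a participant is not aware of his or her HCV diagnosis at the time of enrollment". It then gives the reason for not worrying about it, namely that "participants will be told about the study by their primary HIV provider or self-referred from study flyers that list current chronic HCV infection" as an eligibility criterion, and concludes: "Therefore, it is unlikely that a participant will be unaware of an HCV diagnosis at the time of study enrollment".

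Later in section 8, the Participant Distress paragraph counts on the HIV provider being at hand because recruitment is done at a routine visit.

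Section 4 describes a wider recruitment plan. Its opening summary says: "Information flyers, provider referral, and targeted mailings will be used for recruitment". Under Enrollment, the Recruitment paragraph says that each week "appointments will be reviewed electronically in EPIC to identify HIV/HCV co-infected patients scheduled for primary care visits", and continues: "Letter notifications will be mailed to potentially eligible patients who have an upcoming appointment inviting them to contact the study team". The same paragraph says that eligible participants of a prior study by the same team "who agreed to be contacted for future research (HIPAA form 3) will also be called". It also lists self-referral through trial listings and a research hotline. The Participant Consent paragraph again names the letter as a way into the study.

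**The concern.** The conclusion that unawareness is unlikely is drawn from how people hear about the study. It is sound for a patient whose own HIV provider raises the study. It is also sound for a patient who reads a public flyer and recognises the criteria as applying to them. A letter or a call is different. The team has already identified the recipient, from the record or from an earlier study, and reaches that person away from the clinic.

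Two things are at stake, and the protocol names both among its risks: distress, and loss of confidentiality. The protocol itself describes HCV as often silent for years and poorly understood by patients, so it has reason not to assume awareness. An ethics reviewer relying on section 8 would also be judging a narrower recruitment plan than the one in section 4.

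**Working it through.** No formula applies. The check sets the recruitment routes in section 4 against those in section 8 and then asks whether any other provision fills the gap.

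**Step 1: the routes side by side**

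| Route (section 4) | Who starts the contact | Named in Potential Risks? |
|---|---|---|
| Referral by the HIV provider or clinic staff | Clinic | Yes (as the HIV provider) |
| Clinic flyer or exam-room binder | Patient | Yes (as flyers) |
| Targeted letter | Study team | No |
| Trial listing or research hotline | Patient | No |
| Call to eligible prior-study participant | Study team | No |

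Section 8 uses 2 of 5 routes, so 5 − 2 = 3 are missing. One of these, listings and the hotline, is started by the patient and is of less concern. The other two, letters and calls, are started by the team. The sources for the two differ: letters appear in the section 4 summary, in Recruitment and in Participant Consent, while calls appear only in Recruitment.

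**Step 2: does the section 8 reasoning extend to letters and calls?** The wording of the letter and the call is not in the documents, so both cases have to be considered.

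- If the contact names HCV, a person who then enrols does know of the infection. That knowledge may have come from the contact itself, outside the clinic and possibly in view of others.
- If the contact does not name HCV, the self-screening that section 8 credits to the flyers is missing.

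In neither case does the reasoning given for flyers settle the matter.

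**Step 3: is there a check before contact?** Recruitment has the team approach HIV providers and clinic staff daily for referrals. This is described as a separate source of participants. It is not a condition for sending a letter or making a call. No section requires evidence that the patient has been told of the diagnosis.

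**Step 4: do the other safeguards reach this point?**

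- The distress response in Potential Risks applies during a study visit.
- Participant Distress relies on the HIV provider being present because recruitment is at a regular visit. That does not describe first contact by mail or telephone.
- The Confidentiality measures start once consent is complete. Letters and calls come earlier.
- Participant Consent provides a private area and a comprehension check, both after the patient and the team are in touch. It also warns that a consent form kept by the participant could reveal HIV or HCV status. So the protocol sees a hazard in paper taken home, but states no matching precaution for paper sent home.

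**Result.** The premise in section 8 is incomplete against section 4, and nothing else in the documents covers first contact by letter or call.

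**The case against.** The strongest reply is that section 8 speaks of unawareness at enrolment, not of what a letter might reveal earlier. A letter recipient still has to contact the team, hear the study explained in private, and answer questions on what the study is trying to improve. If the letter lists the HCV criterion as the flyers do, the self-referral logic carries over to enrolment. This stands as far as it goes: letters are not shown to defeat the safeguard at the moment of enrolment. But the letter's content is not given, and a patient who learns of the diagnosis from the letter meets the enrolment test only because the harm has already happened.

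Other mitigation is real but partial. Called patients had agreed to be contacted about future research, all participants must have attended the HIV clinic in the past year, and the research nurse has experience with newly diagnosed patients. None of this shows that a given patient knows the HCV diagnosis before the letter or call.

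A reader might also infer three stronger things that the documents do not support.

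- **That disclosure will happen.** The letter and the call script are not available; they may already be carefully worded.
- **That most of the target group is unaware.** Section 4 reports that 390 of 480 never-attenders had never been scheduled for HCV care, which is 390/480 = 81%. That figure measures scheduling. The protocol explains non-linkage by low perceived need, limited knowledge, competing demands and lack of referral, not by patients never having been told. The pool also differs from the eligible population, which includes earlier attenders with no visit in the past year.
- **That section 8 claims provider and flyer are the sole routes.** It does not say so. Its conclusion simply has no support for the other routes.

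**Conclusion.** The point holds as a gap in participant protection. The protocol's argument that unawareness is unlikely rests on two routes, and its distress provision rests on recruitment at a visit. Letters and calls, the two routes in which the team makes first contact, fall outside both.

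The size of the risk cannot be stated. The documents give neither the share of patients unaware of the diagnosis nor the number to be mailed or called, and no range is offered because nothing in the documents anchors one. The conclusion assumes only that section 4 describes recruitment as it will be run, and that no awareness check exists in material outside these documents.

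There is no effect on the endpoints, the sample size or the analysis. It is more than a wording correction, because the remedy changes what the team does before contacting a patient. It should be made, but it does not threaten the validity of the trial.

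**What to change.** - **Check before contact.** Before any letter is mailed or call made, confirm from the chart or the HIV provider that the patient has been told of the HCV diagnosis.
- **Route the rest through the provider.** Where this cannot be confirmed, the HIV provider should be the only first point of contact.
- **Neutral outer mailings.** Envelopes and anything visible from outside should not point to HIV or HCV. Taking HCV out of the letter itself is a separate choice: it would remove the self-screening that section 8 relies on, so it should not be done without the check above.
- **Correct the text.** Potential Risks and Participant Distress should list every route in section 4, state the check, and drop the premise that recruitment always takes place at a visit.

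The cost is one check per mailed or called patient and a short amendment. For letters, the check fits into the weekly record review and the daily contact with providers that are already planned. Prior-study participants need a separate check, since they may not appear in a review limited to patients with scheduled visits. Whether charts routinely record that a patient has been told is not known; where they do not, the provider has to be asked. Contact with some patients, probably few, will be delayed.

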### **Protection against Risks:**

All study team members will continue to comply with Johns Hopkins and federal human subjects research requirements. All participants will be informed about the potential risks in participating and notified that they can withdraw from the study at any time without penalty.

**Confidentiality:** After participants have completed the necessary consent process and have agreed to enrollment, they will be assigned a unique study identification number. This number will be used to label all study documents. A key for linking participants with their IDs will be necessary to access and link appropriate medical records data to the study ID number. This list will be kept separately from all other study materials in a locked cabinet in a locked office in the School of Nursing. Participants' names will not appear on any records or data collection forms.

As noted, all research information will be kept in locked cabinets, in a secure locked office in the School of Nursing. Access to identifying information will be limited to the approved study team. Participants will be advised of the precautions that will be taken to preserve confidentiality during the consent process. Data with identifiers will not be permitted outside of the Johns Hopkins campus.

All de-identified data collected from study questionnaires and medical record abstraction will be entered into a password protected and encrypted data management system known as REDCap (Research Electronic Data Capture). This is a university developed system that will allow direct online data capture into a password protected, secured server at Johns Hopkins. The development of the database and security of the data and storage are supported by The Johns Hopkins University School of Public Health, a REDCap Consortium member. The database also will provide a reminder system for data entry, facilitate accurate data collection, and ensure confidence in data integrity.

**Data Security:** The REDCap application is hosted on servers administered by the Data Informatics Services Core (DISC) of the Johns Hopkins Biostatistics Center (JHBC). The JHBC servers are protected by both a hardware firewall and a web application firewall. In addition, they have multi-level intrusion detection, network security audits, and secondary hardware on standby for immediate replacement. JHBC administrators connect to the REDCap servers for system administration using a VPN connection and a two-factor authentication method. All data transmitted between the client browser and REDCap web servers are encrypted using an SSL connection. JHBC system administrators regularly monitor server logs and services to ensure that the servers are secured. To access the REDCap website, all users of the REDCap system must have a valid username and password which is generated and maintained by the JHBC administrators on the REDCap server. Each user account has rights that can be granted or denied including: data import, data export, data comparison, data logging, file repository access, user rights assignment, data access groups assignment, lock/unlock records, and super user. In addition, they can be granted read, edit or no data entry rights for each data entry form.

Date: May 8, 2017

Principal Investigator: [name], MPH, NP

Application Number: IRB00081068

**Participant Distress:** All study visits will take place in private areas within the Bartlett Specialty Practice. Procedures for asking sensitive questions have been developed for previous research by [name] and [name] with this population. Distress is unlikely, but may arise during the survey or education; in the case that a participant becomes distressed during a study visit, the research nurse's experience providing care to this population will allow her to effectively approach any such situations. In addition, the participant's HIV primary provider will be available, since recruitment takes place during a regular visit. Further support will be provided by the PI and Co-PI, who are clinicians active in clinical care of people living with HIV and HCV. The study team will be available to participants by phone or email in case participants have further questions or concerns.

### **Plan for Reporting Unanticipated Problems or Study Deviations**

**Data Safety and Monitoring Plan:** A group of designated Johns Hopkins faculty will have responsibility for monitoring and oversight of protocol events for this research. This includes [name] (School of Nursing), [name] (School of Medicine), [name] (School of Nursing), and [name], RN (School of Nursing). The study team will meet biweekly to review recruitment progress, any issues related to data collection, and to ensure that all concerns related to intervention delivery are handled appropriately. Any unanticipated problems or study deviations will be reported to [name] immediately. If there is any concern raised by a participant that the study team cannot address, assistance will be sought through the Institutional Review Board.

## **9. Benefits**

There may be no direct benefit to the subjects in this study; however, information obtained in this study may inform research and practice so that the most effective linkage to care and treatment approach is integrated into the care of this population to decrease morbidity and mortality related to HIV/HCV co-infection. Given the interaction with participants, it is possible that a participant may benefit from more timely evaluation and/or treatment of HCV.

## **10. Payment and Remuneration**

Enrolled participants in both the enhanced usual care and intervention groups will receive a \$20.00 gift card after completion of the baseline study visit. We will offer a second gift card of \$20.00 to participants in the intervention arm on completion of the phase 2 nurse case management visit.

## **11. Costs**

There are no direct costs to the patient in this study.

Date: May 8, 2017

Principal Investigator: [name], MPH, NP

Application Number: IRB00081068

